2.3 Known and Potential Risks and Benefits to Human Subjects

2.3.1 Benefits

No approved prophylactic, post-exposure, or therapeutic treatment modalities exist for SARS-CoV-2. The subjects enrolled in this study have COVID-19 requiring hospital admission, and it is considered that Liquid Alpha 1-PI (Human) may provide therapeutic benefit via its potential anti-inflammatory properties in this critical situation.

One of the primary functions of alpha 1-PI (AAT) in the human body is to irreversibly bind NE. NE is an omnivorous serine protease released by activated or disintegrating neutrophils. NE levels and activity are markedly increased in the airways of patients with ARDS, and previous studies have shown that IV administration of AAT in humans results in augmented anti-elastase capacity of airway epithelial lining fluid, reduced NE activity in bronchoalveolar lavage fluid and decreased breakdown of lung tissue (Campos 2019; Chapman 2015; McElvaney 2017; Wewers 1987). Although these studies were performed in subjects with congenital AAT deficiency. While AAT chiefly inhibits NE, it also other exerts an antiprotease effect on chymotrypsin, cathepsin G (CathG) and proteinase 3 (PR3) (Greene 2009).

In addition to its antiprotease effects (Matheson 1981; Ogushi 1987; Sinden 2015), AAT is a potent anti-inflammatory and immunomodulator (Bergin 2010; Bergin 2014; Hurley 2014; O'Dwyer 2015; Jonigk 2013). Of particular relevance to COVID-19, it has been shown to modulate suppress the production and activity of several key pro-inflammatory cytokines, including interleukin IL-1, IL-6, IL-8 and TNF- α (Bergin 2010; Bergin 2014; Pott 2009; McCarthy 2018), while preserving the production of the anti-inflammatory cytokine IL-10 (Janciauskienė 2007). As such, it is feasible that exogenous administration of alpha 1-PI (AAT) may alleviate the hyperinflammatory component of COVID-19 which can cause accentuating respiratory impairment. For this reason, the current randomized, controlled study in hospitalized

GRIFOLS Bioscience Industrial Group	Number	BIG-CL-PRT-000019
	GC2006 -A Multicenter, Randomized, Open-label, Parallel Group Pilot Study to Evaluate the Safety and Efficacy of Prolastin®-C Liquid plus Standard Medical Treatment (SMT) versus SMT alone in Hospitalized Subjects with COVID-19	
	Version	6.0
	Status	Effective
	Effective Date	08-Dec-2021
	Page	29 of 94

COVID-19 subjects is being undertaken to evaluate whether therapeutic benefit is feasible to attain following IV administration of Liquid Alpha₁-PI (Human).

Decreasing morbidity and mortality remain the theoretical benefit and aim of administration of Liquid Alpha₁-PI (Human) in patients with COVID-19. In this study, therapeutically high doses of Liquid Alpha₁-PI (Human) will be administered to those patients hospitalized with COVID-19 in an effort to reduce their symptoms and improve outcomes by leveraging the modulatory and anti-inflammatory effects of Prolastin described above. These doses are commensurate with prior clinical experience with alpha₁-PI.

2.3.2 Risks

There are no known drug interactions with IV alpha₁-PI. No known drug interactions have been encountered in clinical studies of Prolastin.

Individuals with known selective or severe IgA deficiency who have known antibodies against IgA should not receive Alpha₁-PI since these subjects may experience severe reactions, including anaphylaxis, to IgA which may be present in the preparation.

When medicines are made from human plasma, certain measures are put in place to prevent infections being passed on to patients. These include:

- Careful selection of blood and plasma donors to make sure those at risk of carrying infections is excluded
- The testing of each donation and pools of plasma for signs of virus/infections
- The inclusion of steps in the manufacturing of plasma derivatives with virus inactivation/removal capacity

Despite these measures, when medicines prepared from human blood or plasma are administered, the possibility of passing on infection cannot be totally excluded. This also applies to any unknown or emerging viruses or other types of infections.

In clinical trials the most common adverse reactions observed at a rate of >5% in subjects receiving Liquid Alpha₁-PI were diarrhea and fatigue, each of which occurred at a rate of 6% (two subjects each).

The post-marketing adverse reactions for Prolastin®-C Liquid (the formulation of Liquid Alpha₁-Proteinase Inhibitor used in this study) are as follows:

- General/Body as a whole: fatigue, malaise, influenza-like illness, pain, asthenia
- Immune system: hypersensitivity including anaphylactoid/anaphylactic reactions
- Cardiovascular: tachycardia
- Musculoskeletal: arthralgia, myalgia

GRIFOLS Bioscience Industrial Group	Number	BIG-CL-PRT-000019	Version	6.0	Status	Effective	Effective Date	08-Dec-2021
	GC2006 -A Multicenter, Randomized, Open-label, Parallel Group Pilot Study to Evaluate the Safety and Efficacy of Prolastin®-C Liquid plus Standard Medical Treatment (SMT) versus SMT alone in Hospitalized Subjects with						Page	30 of 94

- Gastrointestinal: vomiting, diarrhea
- Investigation: blood pressure increased

2.4 Description of and Justification for the Route of Administration, Dosage, Dosage Regimen, and Treatment Periods

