- Screening/Baseline (Day 1) during which eligibility criteria are reviewed. Once all eligibility criteria are met and all pre-infusion assessments are completed, blinded Liquid Alpha₁-PI (Human) or Placebo administration can begin as expeditiously as feasible. On Day 8 a second IV dose of blinded Liquid Alpha₁-PI (Human) or Placebo will be administered on Day 8. If the subject has been discharged from the hospital at the time of the Day 8 blinded Liquid Alpha₁-PI (Human) or Placebo infusion, the 2nd infusion is not mandatory, and is at the discretion of the Principal Investigator and subject.
- SMT, Observations, and Follow-up (Days 2 to Day 29): SMT will be provided to all subjects with daily assessments while hospitalized and follow-up from Day 2 through Day 29±1 day (inclusive).
- Phone Checks will occur at Day 60 and Day 90 for vital status (living or deceased), any hospital re-admissions or serious/non-serious adverse events after the Day 29 Final Clinic Visit.

The overall study schema is shown in [Figure 4-1](#).

GRIFOLS	Number	BIG-CL-PRT-000019	Version	6.0	Status	Effective	Effective Date	08-Dec-2021
	GC2006 -A Multicenter, Randomized, Open-label, Parallel Group Pilot Study to Evaluate the Safety and Efficacy of Prolastin®-C Liquid plus Standard Medical Treatment (SMT) versus Bioscience Industrial Group							
								38 of 94

IV = intravenous; SMT = standard medical treatment

*Note: If the subject has been discharged from the hospital at the time of the Day 8 blinded Liquid Alpha-1 PI infusion, the 2nd infusion is not mandatory, and is at the discretion of the Principal Investigator and subject

Figure 4-1 Overall Study Schema

GRIFOLS Bioscience Industrial Group	Number	BIG-CL-PRT-000019	Version	6.0	Status	Effective	Effective Date	08-Dec-2021
	GC2006 -A Multicenter, Randomized, Open-label, Parallel Group Pilot Study to Evaluate the Safety and Efficacy of Prolastin®-C Liquid plus Standard Medical Treatment (SMT) versus SMT alone in Hospitalized Subjects with						Page	39 of 94

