5.2 Exclusion Criteria

A subject meeting any of the following exclusion criteria is NOT eligible for participation in the study.

1. Subjects requiring invasive mechanical ventilation or ICU admission or with PaO₂/FIO₂ \leq 150 mm Hg (i.e., arterial oxygen in mm Hg divided by fraction inspired oxygen concentration [e.g., 0.21 for room air])
2. Clinical evidence of any significant acute or chronic disease that, in the opinion of the investigator, may place the subject at undue medical risk.

GRIFOLS Bioscience Industrial Group	Number	BIG-CL-PRT-000019	Version	6.0	Status	Effective	Effective Date	08-Dec-2021	Page	44 of 94
	GC2006 -A Multicenter, Randomized, Open-label, Parallel Group Pilot Study to Evaluate the Safety and Efficacy of Prolastin®-C Liquid plus Standard Medical Treatment (SMT) versus SMT alone in Hospitalized Subjects with COVID-19									
3. The subject has had a known serious anaphylactic reaction to blood, any blood-derived or plasma product, or known Selective IgA Deficiency with anti-IgA antibodies.										
4. A medical condition in which the infusion of additional fluid is contraindicated (e.g., decompensated congestive heart failure or renal failure with fluid overload). This includes currently uncontrolled congestive heart failure New York Heart Association Class III or IV stage heart failure.										
5. Shock that is unresponsive to fluid challenge and/or multiple vasopressors and accompanied by multiorgan failure considered not able to be reversed by the Principal Investigator										
6. Known alpha-1 antitrypsin deficiency for which the subject is already receiving alpha1-proteinase inhibitor augmentation therapy										
7. Women who are pregnant or breastfeeding. Female subjects of child-bearing potential must have a negative test for pregnancy blood or urine human chorionic gonadotropin (HCG)-based assay at Screening/Baseline Visit.										
8. Subjects for whom there is limitation of therapeutic effort such as “Do not resuscitate” status Note: If the decision is made not to apply treatments or therapeutic procedures that will provide little benefit for the suffering or agony the subject is experiencing, such a subject would not be appropriate for participation in this study and should be excluded.										
9. Currently participating in another interventional clinical trial with investigational medical product or device										

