Subjects randomized to placebo plus SMT will receive sterile 0.9% sodium chloride injection (0.9% NaCl, USP) or equivalent to maintain the blind. The infusion solution will be at a volume commensurate to that required for the appropriate weight-based dose of Liquid Alpha₁-PI (Human) and visually masked to maintain the blind. It will be prepared by the unblinded pharmacist or designee and the infusion bag will be covered with a non-transparent sleeve. In order to maintain the blind, the placebo infusion will be filtered during administration using an IV administration set with a suitable 5 to 15-micron infusion filter (not supplied).

An infusion may be stopped at the discretion of the medical personnel according to normal practice, for instance if there is extravasation at the IV site, and then restarted using a new IV site. However, if a hypersensitivity reaction occurs, such as anaphylaxis, the IV infusion must be stopped permanently, and no further study infusions will be given. During infusion

GRIFOLS	Number	BIG-CL-PRT-000019
	GC2006 -A Multicenter, Randomized, Open-label, Parallel Group Pilot Study to Evaluate the Safety and Efficacy of Prolastin®-CL Liquid plus Standard Medical Treatment (SMT) versus SMT alone in Hospitalized Subjects with	
Bioscience Industrial Group	Version	6.0
	Status	Effective
	Effective Date	08-Dec-2021
	Page	48 of 94

vital signs will be measured and the subject will be carefully observed. Specifically, vital signs will be measured immediately before infusion, then after the first 5 minutes of infusion and subsequently at 5 to 10-minute intervals during infusion until the end of infusion, and at a time point 2 hours after the end of infusion. Early signs and symptoms of hypersensitivity reactions may include pruritus; generalized urticaria; flushing; swollen lips, tongue, or uvula; wheezing; tightness of the chest; dyspnea; hypotension; and syncope. If hypersensitivity symptoms occur, the infusion must be promptly stopped, and appropriate therapy administered. Such subjects who discontinue infusion will be monitored according to standard of care until hypersensitivity/anaphylaxis resolves and will not receive any further IP.

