- Hematology: absolute neutrophil & lymphocyte count and standard hematology (hemoglobin, hematocrit, platelet count, leukocyte count with differential)
- Assessment of ARDS (Berlin Criteria) ([Appendix 3](#))
- Ferritin (serum), D-dimer (plasma, sodium citrate tube), CRP (serum)
- Cytokine panel (IL-1 β , IL-10, IL-6, IL-8, IL-2, interferon γ , and TNF- α). Note: serum samples must be stored at -70° C for later analysis at a reference laboratory.
- Levels of alpha 1-PI (AAT) activity and antigen; both plasma (sodium citrate) and serum samples to be stored at - 70° C for measurement of both antigenic content and functional activity (potency).
- Record SAEs and TEAEs
- Record standard care concomitant medications

After all Screen/Baseline assessments are complete subjects may be randomized.

Subjects may receive the first infusion of blinded Liquid Alpha₁-PI (Human) or Placebo on Screen/Baseline and Randomized Treatment visit (Day 1) if eligibility criteria are met, and all pre-infusion assessments are performed. The intent is for infusion of blinded Liquid Alpha₁-PI (Human) or Placebo to commence as rapidly as feasible on Day 1. If there is unanticipated delay due to pandemic conditions, while not ideal, proceed with the first blinded Liquid Alpha₁-PI (Human) or Placebo infusion as rapidly as possible.

During study infusion vital signs will be measured immediately before the start of infusion, after the first 5 minutes of infusion, and subsequently at 5-10-minute intervals during infusion until the end of infusion. Vital signs will also be measured 2 hours after the end of study infusion.

Record all infusion details and date/time in the CRF on the specific “1st IP infusion day” page and continue with all protocol-specified assessments.

All Study Days are relative to Day 1 (Screen/Baseline and Randomized Treatment visit).

7.2.3 SMT and Daily Evaluations (Days 2 through 10 if still hospitalized) and Mandatory Day 5 Assessments for All Subjects

All subjects receive continued SMT. **On Day 8 all subjects will receive a second double-blind infusion of blinded Liquid Alpha₁-PI (Human) or Placebo. Subjects randomized to Liquid Alpha₁-PI (Human) will receive a second blinded dose of 120 mg/kg body weight. Subjects randomized to Placebo will receive a second blinded infusion of sterile 0.9%**

GRIFOLS Bioscience Industrial Group	Number	BIG-CL-PRT-000019	Version	6.0	Status	Effective	Effective Date	08-Dec-2021

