8.3.1 Warnings/Precautions

Hypersensitivity reactions, including anaphylaxis, may occur. Monitor vital signs and observe the subject carefully throughout the infusion.

Individuals with known selective or severe IgA deficiency who have known antibodies against IgA should not receive Liquid Alpha₁-PI (Human) since these subjects may experience severe reactions, including anaphylaxis, to IgA which may be present in the preparation.

Since Liquid Alpha₁-PI (Human) can cause a transient increase in blood volume, particular caution is necessary in subjects with severe heart failure and subjects at risk of circulatory overload.

When medicines are made from human plasma, certain measures are put in place to prevent infections being passed on to subjects. These include:

- Careful selection of blood and plasma donors to make sure those at risk of carrying infections is excluded
- The testing of each donation and pools of plasma for signs of virus/infections
- The inclusion of steps in the manufacturing of plasma derivatives with virus inactivation/removal capacity

However, despite these measures, when medicines prepared from human blood or plasma are administered, the possibility of passing on infection cannot be totally excluded. This also applies to any unknown or emerging viruses or other types of infections.

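### Exclusion 3 bars known selective IgA deficiency with anti-IgA antibodies, but the protocol's own warnings also cover severe IgA deficiency

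*Protocol*

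**What the plan says.** Protocol 2.3.2 (Risks) states a contraindication: "Individuals with known selective or severe IgA deficiency who have known antibodies against IgA should not receive" the product. The reason given is that IgA may be present in the preparation and could provoke severe reactions, including anaphylaxis. Protocol 8.3.1 (Warnings/Precautions) repeats it for people with "known selective or severe IgA deficiency who have known antibodies against IgA should not receive Liquid" Alpha₁-PI.

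Exclusion 3 has two limbs, worded alike in the synopsis and in 5.2. The first is a known serious anaphylactic reaction to blood or to a blood-derived or plasma product. The second is "known Selective IgA Deficiency with anti-IgA antibodies". The words 'or severe' are missing from both copies.

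Two sections tie the first infusion to the criteria. Section 4.2 allows administration to begin "Once all eligibility criteria are met and all pre-infusion assessments are completed". Section 7.2.2 allows the first infusion "if eligibility criteria are met, and all pre-infusion assessments are performed".

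SAP 3.1 restates no criteria and refers back to Protocol 5.1 and 5.2.

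**The concern.** The warnings and the exclusion criterion address the same hazard but describe different groups, and the criterion describes the smaller one. Under 5.3.1, sites document compliance with each individual criterion, so the numbered list is where a contraindication is reliably checked. A contraindication that appears in full only in the risk and warning sections depends on someone recalling it at the bedside, in a study that wants the first infusion given as fast as is feasible.

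At stake is a subject who is formally eligible and randomized, yet whom the protocol says should not be dosed. If this is noticed before the infusion but after randomization, the dose has to be withheld. The subject stays in the ITT population, which is everyone randomized (9.1), and under 5.3.3 is not replaced if withdrawn. If it is not noticed, the safeguard in 6.1 is reactive: "If hypersensitivity symptoms occur, the infusion must be promptly stopped". Exposure has begun by then. Under 8.5, a Grade 3 hypersensitivity reaction or a serious anaphylactic reaction attributable to the product would also suspend enrollment temporarily.

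**Working it through.** No arithmetic beyond a count applies; the check compares wording.

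**Step 1. Set the two definitions side by side.**

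| Element | Warnings (2.3.2, 8.3.1) | Exclusion 3, IgA limb (synopsis, 5.2) |
|---|---|---|
| Type of IgA deficiency | selective or severe | selective only |
| Is the deficiency a known one? | yes | yes |
| Anti-IgA antibodies | required, and known | required; 'known' not repeated |
| Consequence | should not receive the product | not eligible |

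As logic:
- Warnings: (selective OR severe) AND known anti-IgA antibodies.
- Exclusion 3, IgA limb: selective AND anti-IgA antibodies.

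The deficiency element is narrower in the criterion. The antibody element is, if anything, slightly wider, because it does not repeat 'known'.

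**Step 2. Look for another criterion that covers the difference.** Section 5.1 has 5 inclusion criteria and 5.2 has 22 exclusion criteria: 5 + 22 = 27. Only exclusion 3 names IgA deficiency, so 1 of 27. The wider wording stands in 2 places (2.3.2, 8.3.1) and the narrower in 2 (synopsis, 5.2). These counts describe the text; they do not measure risk.

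**Step 3. Identify who falls between the two.** A subject passes exclusion 3 but falls under the warnings if all of these hold:
1. known severe IgA deficiency;
2. the deficiency is not regarded as selective;
3. known anti-IgA antibodies;
4. no known serious anaphylactic reaction to blood, a blood-derived product or a plasma product, which would trigger the first limb.

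**Step 4. Ask what else would prevent dosing.**
- The statements in 2.3.2 and 8.3.1 still tell sites not to give the product, but they are not eligibility criteria.
- Exclusion 2 covers significant disease that, "in the opinion of the investigator, may place the subject at undue medical risk". It depends on judgment and does not name IgA.
- Sections 5.3 and 5.3.2 let the investigator withdraw a subject, including before infusion, but that comes after enrollment.
- Monitoring and stopping under 6.1 act only once the infusion is running.

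Together these make dosing unlikely. None does what a named criterion does at screening.

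**Step 5. Check for an innocent explanation.** All four places are current protocol text. The wording is complete in each, so neither redaction nor damaged extraction accounts for the missing words.

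**The case against.** The strongest reply is that the gap exists only if severe IgA deficiency with antibodies is a different group from selective IgA deficiency with antibodies. The documents define neither term, and the label 'not selective' is the reviewer's, not the protocol's. On the documents alone, what is proven is a difference in wording. That stands, and it is why the point is rated minor. Against it, the protocol joins the two terms with 'or' in both warnings, and a reader at a site would take that to mean that they are not the same.

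Second, nothing here is a strict contradiction. A site can follow exclusion 3 and still obey 8.3.1, which is part of the protocol and binding on sites. Sections 4.2 and 7.2.2 only permit infusion; they do not require it. This also stands. The defect is that the eligibility list is incomplete against the protocol's own contraindication, not that a site is told to do two incompatible things.

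Third, an investigator who knows of the deficiency and the antibodies, and has read the warnings, has little room under exclusion 2 to judge the risk acceptable. That is fair, and such a subject would probably be caught. It lowers the importance of the point but does not explain why the criterion should stay narrower than the warning.

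Finally, the group needs several conditions to coincide and no size can be given for it. That is conceded.

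**Conclusion.** The inconsistency is real and appears identically in the synopsis and in 5.2. The protocol says twice that people with known selective or severe IgA deficiency and known anti-IgA antibodies should not receive the product, and its only criterion on the subject covers selective deficiency alone.

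Its weight is small. The documents give no prevalence, so no count or rate is claimed, and the affected group is probably very small. The warnings and exclusion 2 would probably prevent dosing. The safety reading assumes that 'selective' and 'severe' are meant as different groups, as the 'or' suggests. If the sponsor means one group, the mismatch is editorial. The primary endpoint, sample size and analysis are unaffected.

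**What to change.** In the synopsis and in 5.2, add 'or severe' to the IgA limb of exclusion 3, so that it reads: *known selective or severe IgA deficiency with anti-IgA antibodies*.

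Do not also insert 'known' before the antibodies to match 2.3.2 and 8.3.1. The present criterion lacks that second qualifier, and adding it could narrow the exclusion. Leave 2.3.2 and 8.3.1 as they are. If 'selective' and 'severe' turn out to mean one group, the added words do no harm.

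The cost is two words in two places. Section 12.2 requires a change to the criteria to go through a protocol amendment, submitted to the regulatory authority and/or ethics committee as applicable, so the sensible route is to carry it in the next amendment. No new screening test is needed, because the criterion already concerns a known deficiency. The SAP needs no edit, since it refers to the protocol for eligibility.

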2.4.1 Administration of Investigational Product

Subjects randomized to the combination arm Liquid Alpha₁-PI (Human) plus standard medical treatment (SMT), will receive IV Liquid Alpha₁-PI (Human) and SMT.

Subjects in the placebo plus SMT arm will receive all standard of care interventions required and Placebo.

